5.3 Packaging, Labelling and Storage

The study packaging and labelling of drug product will be performed by Ora. The storage and distribution supply of drug product will be performed by Ora. All packaging and labelling operations will be performed according to Good Manufacturing Practice for Medicinal Products and the relevant regulatory requirements. [REDACTED]
[REDACTED]
[REDACTED]
[REDACTED]

[REDACTED] All boxes will remain closed except while being accessed by the nominated unmasked personnel administering the real and sham injections.

The Investigator will ensure that the drug product is stored in appropriate conditions [REDACTED]
[REDACTED]
[REDACTED]

[REDACTED] Upon completion of dosing, the used drug product may be destroyed with routine medical waste at the clinical site. The Investigator (or designee) will dispense the drug product only to the identified subjects of this study following the procedures described in this study protocol and documented in the subject dispensing log.

Drug Product inventory/dispensing will be documented in the source documentation and the eCRF for each subject. The Investigator is responsible for all drug products. Written

documentation is mandatory. After completion of the study, all unused drug product will be returned to the location designated by Ora for accountability and destruction.

5.4 Masking and Breaking the Masking

The study will be performed in a double-masked manner. The study is masked by sham procedure and sham packaging. The sham procedure will be identical to injecting study drug, except as described previously, thereby enabling double-masked conditions.

The study mask should not be broken except in a medical emergency (where knowledge of the study drug received would affect the treatment of the emergency) or regulatory requirement (e.g., for SAEs or death). The subject's safety takes priority over any other considerations in determining if a treatment assignment should be unmasked.

Before breaking the mask of an individual subject's treatment, the Investigator should determine that the unmasked information is necessary, i.e., that it will alter the subject's immediate management. In many cases, particularly when the emergency is clearly not related to the study drug, the problem may be properly managed by assuming that the subject is receiving active product. The decision to unmask treatment assignment should be discussed with the Sponsor and Medical Monitor. The Investigator should only call in for emergency unmasking AFTER the decision to discontinue the subject has been made.

If the mask is broken, the date, time, and reason must be recorded in the subject's eCRF system and any associated AE report.

Once approval for unmasking is obtained, the Investigator can unmask study drug assigned to a subject through the IRT system.

If an Investigator, site personnel performing assessments, or subject is unmasked, the subject must be listed as major protocol deviation.

Serious unexpected suspected adverse reactions (SUSARs), which are subject to expedited reporting, should be unmasked before submission to the Regulatory Authorities.

The overall randomization code will be broken only for reporting purposes. This will occur once all final clinical data have been entered onto the database and all data queries have been resolved, and the assignment of subject to the analysis sets has been completed.

5.5 Drug Accountability

The Investigator is responsible for maintaining accurate study drug accountability records throughout the study.

Each dispensing of study drug will be documented in the eCRF.

The Investigator is responsible for returning all unused study drug to Ora at the completion of the study. Ora will ensure no remaining supplies are in the Investigator's possession and agree with the Sponsor the fate of returned study drug.

5.6 Compliance

Study drug shall be administered by qualified unmasked staff at the clinical site; the procedure must be recorded in the eCRF.

5.7 Concomitant Medications/Therapy

The concomitant use of the following medications will not be allowed in the study:

- Anti-VEGF administered systemically;
- Any treatment in the study eye or given intravitreally in the study eye for DME other than the study medication. Note, the fellow (non-study) eye may be treated for DME at the Investigator's discretion;
- Steroid administered systemically, intravitreally in the study eye, or topically in the study eye;
- NSAIDs administered topically in the study eye;
- Any Jetrea® (ocriplasmin) intravitreal injection in the study eye.
- Any ophthalmic medication that in the opinion of the Investigator may influence the interpretation of the safety and/or efficacy parameters in this study.

Details of all medications (other than those intended to treat the study subjects' DME), therapies and supplements administered within 3 months prior to Screening Visit until the end of the study will be recorded in the eCRF. See section 6.3.2.1 for details regarding requirements for data collection relative to DME history and previous treatments and medications. With the exception of ocular medications intended to treat DME, prior medications are defined as those medications taken within 3 months prior to Screening Visit; concomitant medications are defined as those medications ongoing at or started after Day 1.

See section 5.8 regarding the collection of rescue treatment medications as concomitant medication.

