5.8 Rescue Treatment

Rescue intervention (e.g., anti-VEGF, focal/grid macular laser photocoagulation, IVT steroids) may be administered due to worsening DME (i.e., attributable to worsening DME and not another cause) if either of the following occurs and, where possible, after consultation with the Medical Monitor:

- During Treatment Phase
 - Best corrected visual acuity (BCVA) deteriorates 3 lines (15 letters) or more from baseline
 - Central Subfield Thickness (CST) worsening of >100 µm from baseline
- During Follow up Phase (i.e., after Week 16)
 - BCVA deteriorates 3 lines (15 letters) or more from highest BCVA during treatment phase or baseline
 - CST worsening of >100 µm from lowest CST during treatment phase or baseline.

Subjects who receive a rescue intervention in the study eye will be discontinued from further study participation. The Week 24/ED evaluations should be collected prior to study discontinuation and prior to administration of the rescue medication. Details regarding the medications used as rescue treatment must be entered as concomitant medications for the respective study subject.

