11.2 Prior and Concomitant Medications

Prior medications are defined as medications that were stopped within the 3 months prior to Day 1; concomitant medications are defined as those medications ongoing at or started after Day 1. At the Screening Visit, subjects will be asked what medications they are taking, as well as those the subject may have taken but discontinued within the 3 months prior to Visit 1. At each study visit, subjects will be asked what concomitant medications they are currently taking or if there have been any changes to their medications since their first visit.

All prior and concomitant ocular and non-ocular medications will be listed including preferred name, indication, route of administration, start date, stop date, dosage, and frequency of administration. Prior and concomitant medications will be coded using the World Health Organization Drug Dictionary (WHODrug) Global, B3, September 2017 to the appropriate Anatomical Therapeutic Chemical (ATC) classification and WHO generic term.

Counts and percentages of ocular and non-ocular prior and concomitant medications will be summarized separately using ATC classification and preferred name. Summaries will include concomitant ocular medications for each eye (study eye and fellow eye), concomitant non-ocular medications, prior anti-VEGF ocular medications in the study eye, prior non-anti-VEGF ocular medications in the study eye, prior ocular medications in the fellow eye, and prior non-ocular medications. Summaries will be displayed by treatment group and over all subjects. Subjects with multiple medications in the same ATC class or preferred name will be counted only once for that respective ATC class or preferred name.

12. Dosing Compliance and Treatment Exposure

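### Protocol 5.7 allows fellow-eye DME treatment but, as written, exempts DME medications from eCRF entry to the end of the study, which conflicts with the by-eye, by-arm table in SAP 11.2

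*Protocol*

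**What the plan says.** Protocol 5.7 prohibits other DME treatment in the study eye, but adds that "the fellow (non-study) eye may be treated for DME at the Investigator's discretion".

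The recording rule follows. It covers "Details of all medications (other than those intended to treat the study subjects' DME), therapies and supplements" over one continuous period that starts 3 months before Screening and runs "until the end of the study will be recorded in the eCRF". The section then points to 6.3.2.1 for DME history and to 5.8 for rescue: "See section 5.8 regarding the collection of rescue treatment medications as concomitant medication". Section 5.8 supplies that instruction: "Details regarding the medications used as rescue treatment must be entered as concomitant medications for the respective study subject".

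SAP 11.2 plans the reporting: "Summaries will include concomitant ocular medications for each eye (study eye and fellow eye"), displayed by treatment group. The matching output is Table 14.1.4.1, in the FAS. Neither SAP 11.2 nor the table list carries an exception for DME drugs.

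**The concern.** The protocol tells sites what to collect and the SAP tells the programmer what to tabulate. Here the two do not match. A site that applies 5.7 as worded would not enter an anti-VEGF or steroid injection given to the fellow eye during the study. Table 14.1.4.1 would still be produced and would look complete, but it would suggest that little or no fellow-eye DME treatment took place.

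The consequence falls on safety reading. Fellow-eye results are reported by arm throughout the safety section. A change in fellow-eye acuity or thickness, or an ocular event in that eye, is hard to interpret without knowing whether the eye was injected with another drug. The same holds for systemic adverse events, since the exposure would be absent from the record.

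**Working it through.** No arithmetic applies and the plan gives no figure on this point. The check sets the passages side by side.

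1. **Scope of the exemption (Protocol 5.7).** It is defined by purpose: medications meant to treat the subject's DME. It names no eye. It sits in a sentence whose period spans both sides of Day 1, so it is not confined to history. It qualifies medications only. Therapies remain recordable, so fellow-eye laser would plausibly be entered. The gap concerns drugs.

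2. **Does it reach the fellow eye?** A fellow-eye anti-VEGF or steroid injection for DME is a medication intended to treat that subject's DME. Read as written, it is exempt.

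3. **Other collection routes in the protocol.**
   - 6.3.2.1 (DME history) is completed at Screening only, and most of its items concern the study eye. It cannot hold on-study injections.
   - 5.8 covers rescue, which the protocol sets out for the study eye. It does not cover discretionary fellow-eye treatment.
   - 7.2.2.1, 7.2.2.2, 7.2.3.1 and Table 2 have changes in concomitant medication collected at every visit and call. However, 6.3.3 says that prior and concomitant medication is documented as 5.7 describes, so this route leads back to the exemption.

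4. **The definition of concomitant medication (end of the same paragraph in 5.7).** Concomitant medications are those ongoing at, or begun after, Day 1. The DME exception in that sentence is attached to prior medications and is not repeated here. By definition, then, a fellow-eye injection in Week 6 is a concomitant medication, yet the recording sentence says DME medications need not be entered. Section 5.7 is therefore ambiguous within itself, and sites could resolve it differently.

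5. **Can the SAP settle it?** SAP 11.2 has subjects asked about their medications at each visit, lists all ocular medications, and summarizes both eyes by arm. But SAP Section 1 gives the SAP precedence over the protocol's statistical analysis methods, not over its collection instructions. SAP Section 16 records a changed definition of prior medications and does not mention this conflict.

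6. **Outputs affected.**
   - Directly: Table 14.1.4.1.
   - In interpretation: fellow-eye BCVA (SAP 14.2, Table 14.3.4.1), fellow-eye CST (SAP 14.3, Table 14.3.4.2), ocular adverse events by eye (SAP 14.1, for example Table 14.3.1.2.2) and systemic adverse events.
   - Not shown to be affected: efficacy, because SAP 8.1 makes the study eye the unit of analysis.

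**The case against.** The best reply is that the parenthesis was meant only to avoid double entry of DME history, which needs a longer look-back than 3 months and has its own form under 6.3.2.1. Several things support that reading: the cross-reference to 6.3.2.1 comes immediately afterwards, the definition of concomitant medication carries no DME exception, and concomitant medication is reviewed at every contact. The listing shells also include 16.2.4.3.4 (Anti-VEGF Medication Log) and 16.2.4.3.5 (IVT Steroid Use). Unlike the adjacent listings 16.2.4.3.3 and 16.2.4.3.6, their titles are not limited to the study eye, so separate forms may already hold these data.

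It can also be said that the special instruction on rescue drugs proves little. Rescue follows the final evaluation and the subject then leaves the study, so an explicit instruction might be needed whatever the parenthesis means.

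Much of this stands. The intended rule may well be the sensible one, and the rescue instruction is not proof of the literal reading. But the contents of the two listings are not given, and no protocol section requires on-study fellow-eye injections to be entered in them. These points make 5.7 ambiguous; they do not replace its stated instruction.

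A reader might infer that fellow-eye treatment is not captured by arm at all. That goes too far, because SAP 11.2 plans exactly that summary. What is missing is a protocol instruction that guarantees the data behind it.

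**Conclusion.** The point holds as an inconsistency between the protocol's collection rule and the SAP's planned output. Read as written, 5.7 exempts on-study fellow-eye DME drugs from recording, while SAP 11.2 and Table 14.1.4.1 depend on them. How incomplete the table would be rests on two things the documents do not give: how many subjects have the fellow eye treated, and how many sites follow the literal wording. No number is offered. A chance imbalance computed from an assumed treatment rate would describe any unrecorded yes/no factor and would say nothing specific about this trial.

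A reader might also infer that unrecorded fellow-eye anti-VEGF confounds the Week 16 BCVA or CST comparison, since the protocol bars systemic anti-VEGF and systemic steroids. The documents do not support that step. Those restrictions concern systemic administration, the same list in 5.7 expressly permits fellow-eye treatment, and nothing in either document shows an effect of fellow-eye treatment on the study eye. No additional efficacy model follows from this point.

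The correction is worth making because it is nearly free and protects a planned table and the fellow-eye safety summaries.

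**What to change.** In Protocol 5.7, limit the parenthesis to pre-study DME treatment that is captured under 6.3.2.1. Add one sentence requiring any DME medication given to the fellow eye from Day 1 to Week 24 to be entered in the eCRF as a concomitant medication, with agent, route, eye and date. Section 5.7 then agrees with SAP 11.2, and Table 14.1.4.1 can be complete by eye and arm without any change to the table.

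The cost is a small wording change and a few extra eCRF entries for subjects whose fellow eye is treated. It does not alter which treatments are allowed.

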5.8 Rescue Treatment

Rescue intervention (e.g., anti-VEGF, focal/grid macular laser photocoagulation, IVT steroids) may be administered due to worsening DME (i.e., attributable to worsening DME and not another cause) if either of the following occurs and, where possible, after consultation with the Medical Monitor:

- During Treatment Phase
 - Best corrected visual acuity (BCVA) deteriorates 3 lines (15 letters) or more from baseline
 - Central Subfield Thickness (CST) worsening of >100 µm from baseline
- During Follow up Phase (i.e., after Week 16)
 - BCVA deteriorates 3 lines (15 letters) or more from highest BCVA during treatment phase or baseline
 - CST worsening of >100 µm from lowest CST during treatment phase or baseline.

Subjects who receive a rescue intervention in the study eye will be discontinued from further study participation. The Week 24/ED evaluations should be collected prior to study discontinuation and prior to administration of the rescue medication. Details regarding the medications used as rescue treatment must be entered as concomitant medications for the respective study subject.

6 VARIABLES AND METHODS OF ASSESSMENT

6.1 Efficacy Variables

Efficacy variables of interest in this study are:

- BCVA in letters as measured by ETDRS;
- CST in μm as measured by Spectral Domain OCT;
- Retinopathy severity as measured by the DRSS and graded from fundus photography.

6.2 Safety Variables

Safety variables of interest in this study are:

- AEs;
- Ophthalmic and physical findings;
- Laboratory test results (clinical chemistry, hematology, and urinalysis);
- Vital signs (SBP, DBP, PR, and respiratory rate).

6.2.1 Adverse Events

An AE is defined as any untoward medical occurrence associated with the use of an investigational product (IP) in humans, whether or not considered IP-related. An AE can be any unfavorable and unintended sign (e.g., an abnormal laboratory finding), symptom, or disease temporally associated with the use of an investigational product, without any judgment about causality. An AE can arise from any use of the investigational product (e.g. off-label use, use in combination with another drug or medical device) and from any route of administration, formulation, or dose, including an overdose.

All AEs spontaneously reported by the subject and/or in response to an open question from study personnel or revealed by observation, physical examination or other diagnostic procedures will be recorded in the source document and on the appropriate pages of the CRF. Any clinically relevant deterioration in clinical finding is considered an AE and must be recorded. When possible, signs and symptoms indicating a common underlying pathology should be noted as one comprehensive event.

Documentation regarding the AE should be made as to the nature, date of onset, end date, severity, relationship to investigational product, action(s) taken, seriousness, and outcome of any sign or symptom observed by the physician or reported by the patient upon indirect questioning.

6.2.1.1 Severity

Severity of an AE is defined as a qualitative assessment of the degree of intensity of an AE as determined by the investigator or reported to him/her by the patient/subject. The assessment of severity is made irrespective of relationship to investigational product or seriousness of the event and should be evaluated according to the following scale:

- *Mild*: Event is noticeable to the subject, but is easily tolerated and does not interfere with the subject's daily activities.
- *Moderate*: Event is bothersome, possibly requiring additional therapy, and may interfere with the subject's daily activities.

- **Severe:** Event is intolerable, necessitates additional therapy or alteration of therapy, and interferes with the subject's daily activities.

6.2.1.2 Relationship to Investigational Product

The relationship of each AE to the investigational product should be determined by the investigator using these explanations:

- **Suspected:** A reasonable possibility exists that the investigational product caused the AE.
- **Not Suspected:** A reasonable possibility does not exist that the investigational product caused the AE.

Suspected adverse reaction means any AE for which there is a reasonable possibility that the investigational product caused the AE. "Reasonable possibility" means there is evidence to suggest a causal relationship between the investigational product and the AE. Types of evidence that would suggest a causal relationship between the investigational product and the AE include: a single occurrence of an event that is uncommon and known to be strongly associated with investigational product exposure (e.g., angioedema, hepatic injury, Stevens-Johnson Syndrome); one or more occurrences of an event that is not commonly associated with investigational product exposure, but is otherwise uncommon in the population exposed to the investigational product (e.g., tendon rupture); an aggregate analysis of specific events observed in a clinical trial (such as known consequences of the underlying disease or condition under investigation or other events that commonly occur in the study population independent of drug therapy) that indicates those events occur more frequently in the investigational product-treatment group than in a concurrent or historical control group.

6.2.1.3 Expectedness

The expectedness of an AE should be determined based upon existing safety information about the investigational product using these explanations:

- **Unexpected:** an AE that is not listed in the Investigator's Brochure (IB)(IB 2017) or is not listed at the specificity or severity that has been observed.
- **Expected:** an AE that is listed in the IB at the specificity and severity that has been observed.
- **Not applicable:** an AE unrelated to the investigational product.

AEs that are mentioned in the IB as occurring with a class of products or as anticipated from the pharmacological/ mechanical (or other) properties of the product, but are not specifically mentioned as occurring with the particular product under investigation are to be considered unexpected.

The investigator should initially classify the expectedness of an AE, but the final classification is subject to the Medical Monitor's determination.

6.2.1.4 Serious Adverse Events

An AE is considered serious if, in the view of either the Investigator or Sponsor, it results in any of the following outcomes:

- Death;
- A life-threatening AE;
- Note: An AE is considered “life-threatening” if, in the view of either the investigator or sponsor, its occurrence places the patient or subject at immediate risk of death. It does not include an AE that, had it occurred in a more severe form, might have caused death.
- Inpatient hospitalization or prolongation of existing hospitalization;
- Note: The term “inpatient hospitalization” refers to any inpatient admission (even if less than 24 hours). For chronic or long-term inpatients, inpatient admission includes transfer within the hospital to an acute/intensive care inpatient unit. Inpatient hospitalization does not include: emergency room visits; outpatient/same-day/ambulatory procedures; observation/short stay units; rehabilitation facilities; hospice facilities; nursing homes; or clinical research/phase 1 units.
- Note: The term “prolongation of existing hospitalization” refers to any extension of an inpatient hospitalization beyond the stay anticipated or required for the reason for the initial admission as determined by the investigator or treating physician.
- A persistent or significant incapacity or substantial disruption of the ability to conduct normal life functions;
- Note: A serious adverse event (SAE) specifically related to visual threat would be interpreted as any potential impairment or damage to the subject’s eyes (e.g., hemorrhage, retinal detachment, central corneal ulcer or damage to the optic nerve).
- A congenital anomaly/birth defect.

Important medical events that may not result in death, are life-threatening, or require hospitalization may be considered serious when, based upon appropriate medical judgment, they may jeopardize the patient or subject and may require medical or surgical intervention to prevent one of the outcomes listed in this definition.

